	
his/her supplementation must be completed before 1h before bedtime.
 
2. Biological sample collection:
 
The remaining post-test serum samples need to be collected for metabolomics analysis from patients on day 1 of admission, postoperative day 6, postoperative 1 month, postoperative 3 months, and postoperative 6 months.
 
3. Clinical data collection:
 
1) General information: gender, age, height, weight, BMI, ICG 15min retention time, name of surgery, duration of surgery, blood loss, blood transfusion, tumor stage, NRS2002, GLIM malnutrition assessment (diagnostic) criteria diagnosis.
 
2) Nutritional indicators: Nutritional indicators such as serum albumin (ALB), prealbumin (PA), transferrin (TRF), and total serum protein (TP) were collected from patients on the 1st day of admission, the 6th postoperative day, 1 month postoperatively, 3 months postoperatively, and 6 months postoperatively.
 
(3) Liver function indexes: Liver function indexes such as alanine aminotransferase(ALT), alanine transaminase(AST), γ-glutamyltransferase (GGT), cholinesterase (CHE), and total bilirubin (TBIL) were collected on the 1st day of admission, the 6th postoperative day, 1 month postoperatively, 3 months postoperatively, and 6 months postoperatively.
 
(4) Clinical outcome: collect the patients' postoperative clinical outcome indicators, such as: postoperative complication rate, recurrence-free survival, and quality of survival.
 
(5) Medical costs: collect the total cost of the patients' hospitalization, the cost of anti-infective drugs, and the cost of albumin during hospitalization.

Evaluation of the	
Indicators of effectiveness evaluation
 
Main efficacy indicators: serum albumin (ALB)
 
Secondary efficacy indicators: serum prealbumin (PA), alanine

efficacy of treatment	aminotransferase (ALT), azelaic transaminase (AST), cholinesterase (CHE), total bilirubin (TBIL), total hospitalization costs, relapse-free survival, and quality of life
	
Safety evaluation indicators
 
Incidence of gastrointestinal symptoms such as abdominal distension, diarrhea, nausea and vomiting, incidence of postoperative complications, and length of postoperative hospitalization

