All patients were screened for nutritional risk using NRS 2002, nutritional assessment using PG-SGA, and malnutrition diagnosis using GLIM Malnutrition Assessment (Diagnosis) Criteria within 24h of admission. In accordance with the recommendations of ESPEN 2021 Practice Guidelines for Surgical Nutrition Therapy and CSPEN 2016 Guidelines for Perioperative Nutritional Support for Adults, the patients' daily target amount was set at 25-30 kcal/kg. In order to ensure the balanced dietary nutritional intake of the two groups, their standardized management was formulated as follows: ① Total calories: according to the patients' height, weight, age and activity Total calories: Calculate the daily intake according to the patient's height, weight, age and activity intensity, about 1200~2000 kcal. ② Carbohydrates: account for 60%~65% of the actual energy supply, calculate the actual supply of 180~325

g. The staple food is mainly cereals and potatoes. Protein: 1.2~1.5 g/kg/day according to the guideline, choose high quality protein, such as eggs, poultry, soybean products. ④Fat: account for 20% of the actual energy supply, calculate the actual supply of about 27~44 g. Distribute the energy of three meals as 30%, 40%, 30%. According to each patient's required intake, the corresponding nutritional program card is issued, and explained and emphasized at the time of admission and discharge, respectively. Patients could choose different food items on the cards according to their food preferences and actual situation. The experimental group was required to consume LES 1 h before bedtime, while the control group did not consume any food 1 h before bedtime.

Experimental group: patients were given additional meal (total calories 200-275kcal, protein 11.5g-18g, complex carbohydrates 25-55g) 1h before bedtime. the LES regimen was: ① whole protein type enteral nutrition; ② whey protein powder + bread or cookie. The addition of meals was carried out 1h before bedtime. The dietary regimen of the experimental group will be deducted from the corresponding late-evening snacks intake.

(1) Preoperative: ① Patients without nutritional risk: independent intake according to the issued diet program card. ② Patients with nutritional risk: daily oral whole-protein enteral nutrition on the basis of general diet after admission.

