(2) Postoperative: start drinking small amount of water on the 1st postoperative day, over to liquid diet after ventilation, and may over to autonomous semi-liquid diet + oral whole protein enteral nutrition during the day + LES program on the 2nd postoperative day. As the patient's voluntary intake meets 60% of the body's needs, the daytime oral enteral nutrition support can be gradually stopped and the LES program can be continued.

3) Discharge: daily intake needs to be on time according to the LES regimen.

Control group: no more food 1h before bedtime.

(1) Preoperative: same as the test group.

(2) Postoperative: start drinking small amount of water on the 1st postoperative day, over to liquid diet after ventilation, and can over to autonomous semi-liquid diet + oral whole protein type enteral nutrition during the day on the 2nd postoperative day. As the patient's voluntary intake meets 60% of the body's needs, enteral nutrition support can be gradually stopped.

(3) Discharge: Doctors judge whether the patients need to continue nutritional support according to their dietary recovery, and if they do, their nutritional supplementation should be completed before 1h

before bedtime.

2. biological sample collection:

Serum samples remaining after testing were collected from patients for metabolomics analysis.

3.Clinical information collection:

(1) General information collection: gender, age, height, weight, BMI, ICG15min retention time, name of surgery, duration of surgery, blood loss, blood transfusion, tumor stage, NRS2002, PG-SGA, GLIM malnutrition assessment (diagnosis) criteria diagnosis;

(2) Nutritional indicators collection: collect nutritional indicators such as serum albumin (ALB), prealbumin (PA), transferrin (TRF), and total serum protein (TP) on the 1st day of the subject's admission to the hospital, on the 6th day of the postoperative period, at 1 month after the operation, at 3 months after the operation, and at 6 months after the operation.

(3) Collection of liver function indexes: Liver function indexes such as alanine aminotransferase (ALT), alanine grass aminotransferase (AST), γ -glutamyltransferase (GGT), cholinesterase (CHE), and total bilirubin (TBIL) were collected on the first day of hospitalization, the sixth postoperative day, the first postoperative month, the third postoperative month and the sixth postoperative month of the subjects.

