6.4 Medical costs

After the patients were discharged from the hospital, the patients' postoperative length of stay, total hospitalization costs, and drug costs were recorded;

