7.2 Clinical outcomes

1) Post-operative complications

a) Postoperative infections: surgical site infections (SSI), remote infections (RI) and bacteremia.

SSI: Shallow/deep incision SSI and organ/space SSI were defined as redness, swelling, heat, pain, and purulent discharge observed in any incision or space operated on intraoperatively, or the need for a new drain within 30 days postoperatively.

Distant infections: including cholangitis, enteritis, pneumonia, catheter-related infections, and urinary tract infections, defined as fever greater than 38.5°C, leukocytosis, and bacteria detected in

sputum, catheter tips, and urine and feces.

Bacteremia: Bacteremia is diagnosed when a strain is cultured from a single blood culture. And when the strain is identified as coagulase-negative staphylococci, it is considered contaminating; coagulase-negative staphylococci may be considered the causative agent when isolated from two or more blood cultures.

b) Bile leakage

Fluid with a bilirubin concentration of at least three times the serum bilirubin concentration drained through an abdominal drain on or after postoperative day 3. Regardless of the initial bilirubin concentration of the drain placed through surgery, the need for radiologic (i.e., interventional drainage) or surgical intervention (i.e., relative to cesarean section) for biliary collection or biliary peritonitis is also part of the diagnosis of bile leakage.

c) Liver failure after hepatectomy

Elevated serum bilirubin concentration and elevated INR on or after postoperative day 5 compared to the previous day; or coagulation factors such as fresh frozen plasma (FFP) are required to maintain normal INR values on or after postoperative day 5 in combination with hyperbilirubinemia.

- 2) Total hospitalization cost: the total cost of the patient from admission to discharge;
- 3) Recurrence-free survival: the time from the start of the patient's hepatectomy to the first detection of tumor recurrence;
- 4) Quality of Survival: Quality of Survival was evaluated by the EORTC QLQ - HCC18 scale (Appendix 1);
- 5) Safety, diarrhea, vomiting: complaints of gastrointestinal distress that occur after the patient has initiated nutritional support therapy, with diarrhea defined as unformed stools more than three times per day.

8. Adverse Events Watch

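### Total hospitalization cost counts preoperative and operation costs that, under the itemised schedule, precede any difference between the self-chosen groups, and the comparison is unadjusted

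*Combined protocol and SAP*

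**What the plan says.** **Role.** The synopsis names "total hospitalization costs, relapse-free survival, and quality of life" among the secondary efficacy indicators. Section 5.1, item 5, compares hospitalization cost between groups to judge whether outcomes improve under the snack.

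**Window.** The synopsis item on medical costs says to "collect the total cost of the patients' hospitalization" but sets no limits. Section 7.2, item 2, sets them: "the total cost of the patient from admission to discharge". Section 6.4 adds that "postoperative length of stay, total hospitalization costs, and drug costs were recorded". So length of stay is confined to the postoperative period, and cost is not.

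**Start of the group difference.** For the test group, the itemised schedule in section 3.2 first mentions the snack after surgery: "oral whole protein enteral nutrition during the day + LES program on the 2nd postoperative day". The control list opens with "1) Preoperative: same as the test group". A general rule in the same section gives no start day: "The experimental group was required to consume LES 1 h before bedtime". The synopsis has the same two layers.

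**Allocation and analysis.** Section 3.1 describes a non-randomised, open study in which patients join a group by preference. Sections 5.1 and 10 give only unadjusted two-group tests. Name and duration of surgery, blood loss, transfusion and tumor stage are collected (section 3.2), but no analysis uses them.

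**The concern.** An efficacy indicator should cover the period in which the intervention can act. Here the window opens at admission, so preoperative days, work-up and the operation are all in the total. Under the itemised schedule, none of these can be changed by a snack that starts after surgery.

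Two consequences follow. If the groups have similar surgery and preoperative stay, this part of the bill is noise that can hide a real postoperative saving. If they differ, which self-selection permits, the difference enters the estimated effect of the snack on cost one for one, and nothing in the analysis removes it.

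The window also closes at discharge while the test group continues the snack, so the result can speak only to in-hospital cost.

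**Working it through.** **The plan's own figures.** The documents give no cost level, SD, expected effect or sample size for cost. The only planned size is for albumin: 34.2 (SD 3.9) against 37.5 (SD 5.4) g/L, two-sided alpha 0.05, power 90%. With a difference of 3.3 and SD = √((3.9² + 5.4²)/2) = 4.71, the unequal-variance t-test has power 89.4% at 43 per group and 90.07% at 44. The stated 88 (44 per group) therefore reproduces, and 44 is used below.

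**Step 1: window against exposure, on the itemised schedule.**

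| Period | Counted in cost? | Can groups differ because of the snack? |
|---|---|---|
| Admission to operation | Yes | No, preoperative care is the same |
| Operation to postoperative day 1 | Yes | No, the snack is first named on day 2 |
| Day 2 to discharge | Yes | Yes |
| After discharge | No | Yes |

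**Step 2: noise, if the groups are balanced (illustrative).** Let f be the share of the variance of total cost that arises before the snack, assumed independent of later cost. Then SD(total)/SD(later) = 1/√(1 − f). Assume a true effect of 0.5 SD on later cost. On total cost it becomes d = 0.5 × √(1 − f), and power with 44 per group is approximately Φ(d × √22 − 1.96).

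| f | Inflation of detectable difference | d | Power |
|---|---|---|---|
| 0 | 1.00 | 0.500 | 65% |
| 0.25 | 1.15 | 0.433 | 53% |
| 0.50 | 1.41 | 0.354 | 38% |
| 0.75 | 2.00 | 0.250 | 22% |

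**Step 3: bias, if the groups differ (illustrative).** Assume no snack effect. Let the groups differ by p in the share having a costlier resection, and let that resection add c SD to cost. The bias is b = p × c. With standard error √(2/44) = 0.213, the false-positive rate is 1 − Φ(1.96 − b/0.213) + Φ(−1.96 − b/0.213).

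| Imbalance p | c = 0.5 | c = 1.0 | c = 1.5 |
|---|---|---|---|
| 10 points | 5.6% | 7.6% | 10.8% |
| 20 points | 7.6% | 15.5% | 29.1% |
| 30 points | 10.8% | 29.1% | 56.0% |

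Every f, p and c, and the 0.5 SD effect, is an assumption.

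**Step 4: end of the window.** Section 3.2 continues the snack daily after discharge, and section 6.1 follows intake to 6 months. Assume snacks run to day 180, about 180 − 2 = 178 nights. Discharge on day 7 leaves 5 nights inside the window (97% after it); discharge on day 21 leaves 19 (89% after it). The discharge days are assumed. These are counts of nights, not of cost.

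**The case against.** **Surgery need not dominate.** A reader might infer that the endpoint measures the operation more than the snack. The documents do not support that: they give no cost breakdown, no surgical mix by group, and no link between patient wish and type of resection. The window still covers the rest of the postoperative stay, where savings through complications, drugs or length of stay would appear. Section 4.4 also removes some patients with extreme operative events. This objection stands in full.

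**The start day is not settled.** The general rule could be read as starting at admission, and the day-2 step is worded as permitted rather than fixed. The itemised schedule, with its identical preoperative care, favours a postoperative start, but the passages do conflict. If the snack began at admission, preoperative days would no longer be free of it; the operation items would remain.

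**Moving the window does not remove confounding.** Type of resection can also drive postoperative cost. This stands, and it is why adjustment has to accompany the new window. It also makes the independence assumed in step 2 doubtful.

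**The omitted snack cost may be small.** Because most snack nights fall after discharge, a reader might infer that most of the intervention's cost is left out. That does not follow. The snack is deducted from the day's diet, so displaced food offsets part of its cost, and controls may also continue supplements at home. The plan states no net-cost aim.

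**Related measures are already collected.** Anti-infective and albumin costs and postoperative stay are recorded and are closer to the postoperative course. They lessen the problem but do not change what the listed cost indicator compares.

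**Conclusion.** The point holds in a limited form. On the itemised schedule, a secondary efficacy indicator includes costs incurred before the groups can differ because of the snack, and it is compared without adjustment between self-chosen groups. Those costs are noise under balance and direct bias under imbalance.

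The size is unknown. The inflation of 1.15 to 2.00 and the false-positive rates of 5.6% to 56.0% only show how the result would respond to assumed inputs. The conclusion rests on the postoperative start in the itemised schedule; an admission start would narrow it to the operation items. Cost is one of several secondary indicators and is absent from the hypothesis in section 2.3, so this is a minor improvement.

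**What to change.** 1. In the synopsis and sections 5.1, 6.4 and 7.2, make the between-group comparison on postoperative in-hospital cost up to discharge. Count it from the actual snack start in the test group and the matching postoperative day in controls, or take the total minus preoperative and operation items. The subtraction depends least on the start day and suits bills that cannot be split by day.
2. Report total hospitalization cost alongside, as a descriptive figure.
3. Adjust the comparison for the covariates already collected: name of surgery (grouped into a few categories), duration, blood loss, transfusion and tumor stage. Use transfusion only up to the end of surgery, so that the model does not adjust for something that happens after the snack starts.
4. State that the conclusion concerns in-hospital cost only.
5. Reconcile the general snack rule with the itemised schedule, in both the synopsis and section 3.2, so that the cost window and the intervention share one start.

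The cost is wording changes, somewhat more bill extraction, and a compared figure that is less comparable with published totals; reporting the total alongside limits that loss. The plan already extracts some item costs, although that does not show that every bill can be split by day.

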2.1 Primary purpose

To observe the effects of late-evening snacks on the nutritional status, liver function recovery, complication rate and long-term prognosis of hepatocellular carcinoma patients who underwent hepatectomy, and to further explore the effects of late-evening snacks on the metabolic pattern of the patients through metabolomics, and to identify the serum differential metabolites, in order to initially investigate the potential mechanism of late-evening snacks to improve the nutritional status of the patients, and to provide theoretical basis for the development of an effective nutritional regimen in the clinic.

2.2 Secondary purpose

The sample size can be enlarged to continue the population study, to verify and continue to optimize the test results obtained from the validation, to shift from a single-center study to a multi-center study, and to establish an expandable multi-dimensional database. In order to propose a more reasonable nutritional support strategy for the clinic and provide reference for doctors' clinical decision-making.

2.3 Test hypothesis

It was hypothesized that there would be significant differences in serum albumin, prealbumin, and serum metabolic patterns in subjects in the test group compared to control patients, and potential mechanisms by which the LES would improve the nutritional status of patients would be identified.

3. Types of Research Designs and Experimental Steps

3.1 Types of Research Designs

Types of study designs: single-center, prospective cohort studies

Research Center: Drum Tower Hospital, Medical School of Nanjing University

Grouping method: non-randomized, open, enrolled according to patients' wishes

[figure not shown]
Sample size calculation basis and formula:

This study was a single-center prospective cohort study with two groups, the test group and the control group, and the serum albumin level of the study subjects was the primary endpoint outcome indicator observed. Based on the review of previous literature^[28] and reference to the results of the pretest, it was expected that the albumin level before LES intervention was 34.2 ± 3.9 g/L and the albumin level

after LES intervention was 37.5 ± 5.4 g/L, with a two-sided $\alpha=0.05$ and a degree of certainty of $1-\beta=90\%$. Using PASS15 software can be calculated to obtain $n=88$ cases. Based on the 1:1 grouping, 44 subjects were needed in each of the test and control groups, and assuming a 20% subject dropout rate, the final minimum number of subjects needed was 53 in each of the test and control groups, for a total of at least 106 subjects included.

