At the same time, the liver serves as the target organ for the metabolism of most nutrients, and the high metabolic status and organ invasion of cancer often expose liver cancer patients to malnutrition, with an incidence rate as high as 74.36% according to a survey ^[7]. In addition, hepatic resection will cause hepatocyte damage to a certain extent, resulting in the metabolic balance of sugar, protein, fat and hormones in the patient's body being disrupted, which makes the body's catabolism stronger than anabolism ^[8], and it is more likely to have a decrease in the level of albumin synthesis and a significant decrease in the intake of nutrients after the operation, which in turn results in the decrease in the patient's ability to resist infection, the increase in the risk of complications, and the decrease in the quality of life and a series of other poor prognosis ^[9,10,11,12], therefore, nutritional support and intervention are particularly important in this situation. According to our previous study, we found that nutritional intervention by clinical pharmacists in perioperative liver cancer hepatectomy patients could reduce the complication rate by 69%, as well as correct the inflammatory stress response and improve albumin levels more quickly ^[13].

Therefore, we believe that the use of rational and effective nutritional intervention strategies will bring positive benefits to patients.

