(4) Clinical outcome collection: to collect clinical outcome indicators of subjects after surgery, such as: postoperative complication rate, recurrence rate, recurrence-free survival, quality of life.

5) Medical cost collection: to collect subjects' total hospitalization cost, cost of anti-infective drugs, cost of albumin during hospitalization.

Data analysis:

Descriptive statistics were performed on the clinical data, and the measures that conformed to normal distribution were expressed as mean \pm standard deviation ($\bar{x} \pm s$), and the t-test was used between the groups, and the measures that did not conform to normal distribution were expressed as median (interquartile spacing) [M(IQR)], and the Mann-Whitney U test was used between the groups. Count data were expressed as percentages [n(%)], and the chi-square test was used for between-group comparisons, with $P < 0.05$ considered statistically significant. The Kaplan-Meier method in STATA 12.0 was used to calculate the recurrence rate and recurrence-free survival in each group, and the log-rank test was used for intergroup comparison.

4. Case selection

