4.4 Exclusion criteria

Enrolled cases but meeting one of the following should be excluded:

- 1) Intraoperative exploration of the tumor has undergone dissemination or is unresectable;
- 2) Serious intraoperative or postoperative complications of surgical technique within 24h: bleeding or gastrointestinal leakage leading to shock;
- 3) Serious cardiac, pulmonary, cerebral or renal vital organ accidents or insufficiency during the operation or within 24h after the operation;
- 4) Postoperative pathology suggesting non-primary or metastatic hepatocellular carcinoma;
- 5) Patients in the control group who had more than 7 additional meals before bedtime;
- 6) Patients in the test group who did not have more than 7 bedtime refills during the follow-up period;
- 7) Those who voluntarily withdrew.

5. Research Methodology and Technical Approach

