6.2 Nutrition indicators

Serum albumin (ALB), prealbumin (PA), total serum protein (TP), and transferrin were collected from subjects on day 1 of admission, day 6 postoperatively, 1 month postoperatively, 3 months postoperatively, and 6 months postoperatively.

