7.1 Nutritional indicators

Primary Efficacy Indicator:

Serum albumin (ALB), recording ALB data from patient biochemical tests.

Secondary efficacy indicators:

Prealbumin (PA), alanine aminotransferase (ALT), glutamate aminotransferase (AST), serum gamma-glutamyl transpeptidase (GGT), cholinesterase (CHE), total bilirubin (TBIL), and C-reactive protein (CRP) were recorded, and the corresponding data in the patient's biochemical tests were recorded;

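### Sample size: 53 per group covers about 17% loss, not 20%, and the 3.3 g/L difference is a before/after contrast with no control value or visit stated

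*Combined protocol and SAP*

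**What the plan says.** The sample-size paragraph in section 3.1 makes serum albumin the primary endpoint and gives two values, citing reference [28] and a pretest. The first, 34.2 ± 3.9 g/L, is introduced with the words "it was expected that the albumin level before LES intervention was"; the second, 37.5 ± 5.4 g/L, is the level after the intervention. With two-sided alpha 0.05 and 90% power, PASS 15 returns 88, or 44 per group at 1:1. Then, "assuming a 20% subject dropout rate, the final minimum number of subjects needed was 53 in each of the test and control groups". The enrolment floor becomes 106. No formula is given for the dropout step.

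The hypothesis in section 2.3 is between groups: "there would be significant differences in serum albumin, prealbumin, and serum metabolic patterns in subjects in the test group compared to control patients". So is the planned test; section 3.2 says "the t-test was used between the groups", and section 10 repeats it. Section 6.2 says albumin and the other nutrition markers "were collected from subjects on day 1 of admission, day 6 postoperatively, 1 month postoperatively, 3 months postoperatively, and 6 months postoperatively". Section 7.1 defines the primary indicator only as "Serum albumin (ALB), recording ALB data from patient biochemical tests", with no time point.

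The second list in section 4.4 opens "Enrolled cases but meeting one of the following should be excluded". It removes patients after enrolment for, among other reasons, unresectable tumour, unsuitable pathology, departures from the assigned bedtime regimen, and voluntary withdrawal.

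**The concern.** There are two separate issues in one paragraph.

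1. **Dropout step.** If 20% of enrolled patients are lost, 80% of 53 is fewer than 44, so the sentence contradicts its own target. The plan also does not say whether the 20% includes the section 4.4 removals.

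2. **Effect size.** A before/after change in patients who take the snack is not a difference between test and control. Using it as one assumes that controls sit at the before-snack value, with the before-snack SD, at whichever visit is analysed. The plan neither says nor justifies this. The postoperative visits run from day 6 to 6 months, and one control value cannot be presumed to hold at all of them.

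This paragraph is the only stated justification for the size of the trial. As it stands, a reader cannot tell what between-group difference the study is sized to detect.

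**Working it through.** **Inputs (all from section 3.1).** Means 34.2 and 37.5 g/L; SDs 3.9 and 5.4; two-sided alpha 0.05; power 90%; 44 per group; 20% dropout; 53 per group. Difference = 37.5 − 34.2 = 3.3 g/L.

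**Step 1: reproduce the plan's 88.** I treated the two values as independent groups and used the unequal-variance two-sample t-test (noncentral t), with SE = √[(3.9² + 5.4²)/n].
- n = 44: SE = √(44.37/44) = 1.004; 3.3/1.004 = 3.29; power 90.07%.
- n = 43: power 89.4%.

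So 44 is the smallest n per group that reaches 90%, and 88 reproduces. A paired before/after test does not give 88: it needs 45 pairs at correlation 0 and 25 at 0.5, in a single group. The calculation therefore used the before-snack value as the control mean.

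**Step 2: dropout.**
- 44 × 1.2 = 52.8, rounded up to 53 (matches the plan).
- 44/(1 − 0.20) = 55 per group, 110 in total, which is 4 more than 106.
- 53 × 0.80 = 42.4, so about 42 per group remain.
- 1 − 44/53 = 17.0%, the largest loss that still leaves 44.

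Power on the plan's own means and SDs (25% and 30% are my assumptions, to show the effect if section 4.4 removals come on top of the 20%):

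| Loss from 53 | Remaining per group | Power |
|---|---|---|
| 17% | 44 | 90.1% |
| 20% | 42 | 88.7% |
| 25% | 39 | 86.2% |
| 30% | 37 | 84.4% |

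**Step 3: sensitivity to the unstated control value.** 42 per group, test mean held at 37.5, SDs 3.9 and 5.4. The control means other than 34.2 are assumptions.

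| Control mean (g/L) | Difference (g/L) | Power |
|---|---|---|
| 35.7 | 1.8 | 41% |
| 35.2 | 2.3 | 60% |
| 34.7 | 2.8 | 77% |
| 34.2 | 3.3 | 89% |
| 33.7 | 3.8 | 95% |
| 33.2 | 4.3 | 98% |
| 32.7 | 4.8 | 99.6% |

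The SD matters too. For 3.3 g/L at 42 per group, power is 79% with SD 5.4 in both groups and 97% with SD 3.9 in both.

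**Step 4: does the plan settle the direction?** No. Section 3.2 gives controls the same diet standards and allows them daytime enteral nutrition, which could raise albumin. The background in section 1 points the other way: after hepatectomy "it is more likely to have a decrease in the level of albumin synthesis", and a cited chemoembolization study is said to show that the snack prevented an albumin decline.

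**Step 5: detectable difference at 42 per group.**

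| SDs | 80% power | 90% power |
|---|---|---|
| 3.9 and 5.4 | 2.92 g/L | 3.38 g/L |
| 5.4 in both | 3.34 g/L | 3.87 g/L |
| 3.9 in both | 2.41 g/L | 2.79 g/L |

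**Step 6: source of the values.** Reference [28] is, by its title, a guideline on perioperative nutritional support, and the pretest is not described. The origin of the two albumin values cannot be traced from the plan.

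**The case against.** The strongest reply is that the arithmetic slip is trivial. It costs 4 patients and 1.4 power points, the plan calls 53 a minimum and 106 a lower bound, and 88 itself is right. That stands: the dropout error alone would be minor, and I do not ask for more patients. The multiplication by 1.2 is also inferred, though the shortfall from 44 does not depend on how 53 was reached.

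On the effect size, it is fair to say that the control shifts in step 3 are illustrative. Shared care and the effect of surgery act on both groups, so holding the test mean at 37.5 is itself an assumption. The table shows sensitivity, not a demonstrated loss of power. Taking a pre-intervention value as the expected control value may also be reasonable, but then the plan should say so and justify it.

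Three smaller points also stand. Voluntary withdrawal is dropout in the ordinary sense, so only the other section 4.4 removals are unclear. The citation may be a numbering slip. A figure just above the sample-size text is missing from the copy reviewed, so the absence of a control value is established for the readable text only.

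None of this supplies an expected control albumin or a primary visit.

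**Conclusion.** Both parts hold. The dropout statement is wrong as written: 53 per group preserves 44 only up to 17.0% loss, and at 20% loss about 42 remain, with 88.7% power instead of 90.1% on the plan's own means and SDs. The size of this is small.

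The effect basis matters more. The 90% is conditional on a control mean of 34.2 g/L and SD of 3.9 at an unnamed visit, and the plan does not state that condition. The claim is unsupported, not disproved. True power cannot be computed from the documents and could lie well below or above 90%. I am confident about the dropout arithmetic and the missing control value and visit. The other power figures rest on the assumed control means, SDs and loss rates shown.

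**What to change.** Keep 106 patients and revise the sample-size paragraph.

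1. **Loss allowance.** State that 53 per group allows for 17% loss. With 20% loss, 42 per group remain, giving 88.7% power if the between-group difference is 3.3 g/L with SDs 3.9 and 5.4.
2. **Primary visit and effect.** Name one postoperative albumin visit (day 6, or 1, 3 or 6 months) as primary, before any albumin data are examined. Give expected control and test means and SDs at that visit, sourced from the literature or the pretest and not from this study's own data, and recompute power.
3. **If no control expectation is available.** Replace the 90% claim, and the conditional power in item 1, with the detectable difference at 42 per group: about 2.9 g/L at 80% power and 3.4 g/L at 90% (SDs 3.9 and 5.4).
4. **Definition of loss.** Say whether the 20% includes the section 4.4 removals.
5. **Source.** Confirm or correct reference [28] for the albumin values.

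The cost is one rewritten paragraph and one decision on the primary visit, which tightens the endpoint definition and should be carried into section 7.1. No extra patients are needed. The stated power becomes slightly less favourable and may change again once a control value is given.
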